8.2 Statistical analysis of the secondary efficacy variable(s)

8.2.1 Percent reduction in partial seizure frequency

1.31101 Percent reduction from Baseline to the Treatment Period in partial seizure frequency will be calculated by subtracting 28-day adjusted Treatment Period partial seizure frequency [A] from 28-day adjusted Baseline Period partial seizure frequency [B], and multiplying the resulting quantity by 100 and dividing by the Baseline Period 28-day adjusted partial seizure frequency.

%Reduction =
$$100 \times \frac{[B] - [A]}{[B]}$$

Percent reduction in partial seizure frequency from Baseline to the Treatment Period as well as [A], [B] and [B]-[A] will be summarized with quantitative descriptive statistics. Statistical comparisons between each BRV treatment group and PBO will be based on a Wilcoxon-Mann-Whitney test. Hodges-Lehmann non-parametric effect estimates and corresponding two-sided 95% CIs will be provided for the effect difference between each BRV treatment group versus PBO.

Plots displaying the complementary cumulative distribution function for percent reduction from Baseline to the Treatment Period will be provided.

50% responder rate in partial seizure frequency 8.2.2

The 50% responder outcome will be evaluated based on percent reduction in partial seizure frequency per 28 days from Baseline to the Treatment Period. A subject with at least a 50% reduction in 28-day adjusted partial seizure frequency is classified as a responder.

50% Responder Rate (%) = $\frac{\text{Number of 50\% responders}}{\text{Number of subjects in the analysis set}} \times 100$

The number and rate (%) of the responders for each treatment group will be summarized with the corresponding 95% CI for the rate. The CIs will be calculated by an exact method for the binomial distribution (ie, Clopper-Pearson interval).

Statistical comparisons between each BRV treatment group and PBO will be conducted with logistic regression (based on Firth's penalized maximum likelihood inferences). The logistic regression analysis will be done for the event (50% reduction or more) with the predictors described in Section 8.1.2. If the model does not converge or does not produce the estimates, the covariates may be modified. An odds ratio of BRV/PBO for each BRV treatment group will be estimated with its profile-likelihood 95% CI. Both multiplicity-adjusted and unadjusted p-values for the Wald chi-square test for treatment effect will be given.

In addition, 50% responder outcome will be evaluated for the PPS as described above.

8.2.3 Categorized percent reduction in partial seizure frequency

The number and percentage of subjects within each of the following categories of percent reduction in partial seizure frequency from Baseline to the Treatment Period will be summarized for each treatment group: <-25%, -25% to <25%, 25% to <50%, 50% to <75%, 75% to <100%, and 100%. Statistical comparisons between each BRV treatment group and PBO will be based on a Mantel-Haenszel test for the comparison of row mean scores.

8.2.4 Seizure freedom (partial, all epileptic seizure)

Seizure freedom will be assessed separately for partial seizure and for all epileptic seizure.

12til01 A subject is defined as all epileptic seizure free over the Treatment Period if they meet all of the following criteria.

- 1. The subject completed the Treatment Period
- 2. The subject did not have any missing days in the DRC during the Treatment Period, and
- 3. The subject did not report any seizures during the Treatment Period

The algorithm rules for all epileptic seizure freedom are described in Section

The number and percentage of subjects who are seizure free for partial seizure and for all seizure types over the Treatment Period will be summarized.

Additionally, the number and percentage of subjects who met each individual criterion will be summarized, irrespective of whether the other criteria were met. Furthermore, the number and percentage of subjects meeting criteria 2 and 3 but not meeting criterion 1 (ie, subjects without seizures and without missing days in the DRC but discontinued) will be summarized.

Seizure freedom rates for all seizure types will be compared between each BRV treatment group and PBO using Fisher's Exact Test.

The analysis above will be repeated for partial seizure instead of all epileptic seizure (also refer to Section 3.9.4.2).

Seizure frequency for all seizure types 8.2.5

Estimates of percent reduction over PBO and odds ratios for 50% responder rates and corresponding two-sided 95% CIs for seizure frequency for all seizure types (I+II+III) will be provided based on the statistical methodology described in Section 8.1.1, Section 8.1.2 and Section 8.2.2. Additionally, percent reduction from Baseline in seizure frequency for all seizure types will be analyzed as described in Section 8.2.1. Statistical treatment group comparisons will also be provided as described in these sections. In addition, seizure frequency will be listed by subject, study period and seizure type. The data from the DRC will also be listed by subject and study period.

Time to nth partial seizure 8.2.6

The algorithm rules for time to n^{th} partial seizure are described in Section 3.9.5.

Median time to n^{th} seizure and corresponding 95% CIs will be provided based on Kaplan–Meier (KM) estimation. KM plots will be provided for time to n^{th} partial seizure (n=1, 5, 10).

Time to n^{th} partial seizure will be compared between each BRV treatment group and PBO using a semi-parametric proportional hazards regression model with an effect for country, an effect for the 4 combinations of actual stratification levels for LEV status and number of previous AEDs $(\leq 2 \text{ versus } > 2)$ per the CRF data, and log-transformed Baseline partial seizure frequency as a continuous covariate. Significance probabilities (ie, p-values) and hazard ratios and

corresponding two-sided 95% CIs will be presented for the comparison of each BRV treatment group to PBO. Lower enrolling countries will be pooled for this analysis as described in Section 4.1.

9 PHARMACOKINETICS

orization In addition to the following analyses for PK, population PK and/or PK/PD analyses will be considered as needed and described in a separate data analysis plan.

9.1 **BRV** plasma concentrations

The daily dose information for PK analysis will be calculated according to the "Last Dosage Amount" from the CRF form: "BRV Plasma Level Monitoring":

- If the last dosage amount is 25mg/dose, the total daily dose will be 50mg/day
- If the last dosage amount is 100mg/dose, the total daily dose will be 200mg/day
- In case the subjects enter the Transition Period (Visit 8), the last dosage amount can be 75mg/day and the total daily dose will be 150mg/day.

Descriptive statistics in Section 3.1.1 for BRV observed plasma concentrations are computed per defined time window post-dose (>0-4 hours, >4-8 hours, and >8 hours, based on the date and time of last intake of IMP prior to blood sampling) for all PK-PPS by actual dose given before each blood sampling for PK and dose normalized BRV plasma concentrations are computed for all doses with the same manner. The statistics are calculated only if at least 2/3 of the individual data at a specific sampling point are above or equal to the LLOQ.

Figures of the geometric means of BRV observed concentrations versus median time are presented by actual dose given before each blood sampling for PK and by visit. Median time will be calculated separately by each time window post-dose (>0-4 hours, >4-8 hours, and >8 hours). Daily dose normalized (to 50mg) BRV plasma concentrations will be presented with the same manner.

Figures of individual observed BRV plasma concentrations versus time after the last intake of IMP prior to blood sampling will be presented by actual dose given before each blood sampling for PK and by visit. Dose normalized (to 50mg) BRV plasma concentrations will be presented with the same manner.

Furthermore, above analyses are repeated for Japanese and Non-Japanese.

A subject data listing of BRV Plasma Concentration Monitoring covers

- Treatment Group
- Site-Subject Number

Gender/Age(years)/Race/Weight(kg)

- Visit
- Not Done (with a flag 'ND')
- Last dose of study medication prior to Blood Sampling: (Datetime) (yyyy-mmddThh:mm)/Relative Day

- Blood Sampling Datetime (yyyy-mm-ddThh:mm:ss)/Relative Hours to Last Medication
- Last Dose (mg/day)
- Plasma BRV Concentration (µg/mL)
- Time Window [>0-4 hours, >4-8 hours, and >8 hours post dosing]
- Dose Normalized Plasma Level (µg/mL/50mg): equivalent to 50mg/day

SAFETY ANALYSES 10

orization Safety is assessed with AEs, laboratory tests (blood chemistry, hematology, urinalysis, and pregnancy test), vital signs, body weight, ECGs, physical examination, neurological (examination, mental status, and psychiatric status. Summary tables will be provided for AEs; blood chemistry, hematology, and urinalysis; vital signs; body weight; and ECGs. No summary tables will be provided for pregnancy testing, physical examination, neurological examination, mental status, or psychiatric status.

All safety summaries will be based on the SS.

Regarding safety for the Open-Label Temporary Period, it will be summarized separately from other preceding study periods as described in Section 3.2.2.

10.1 **Extent of exposure**

The duration of study medication exposure for the Treatment Period will be calculated as the date of last dose of IMP during the Treatment Period minus the date of first dose of IMP plus 1 day. The overall duration of study medication exposure for the entire study will be calculated as the date of last dose of IMP minus the date of first dose of IMP plus 1 day.

The duration of study medication exposure and the overall duration of IMP exposure will be summarized with quantitative descriptive statistics for the Treatment Period and for the entire study (except the Open-Label Temporary Period), respectively, for the SS. The number and percentage of subjects with the following categories of durations of study medication exposure for the Treatment Period and the entire study will also be summarized:>0 weeks, >=2 weeks, >=4 weeks, >=6 weeks, >=8 weeks, >=10 weeks, and >=12 weeks.

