# 2.2 Background information regarding product

Brivaracetam is a chemical relative of the AED LEV (Keppra®/E-Keppra®). Like LEV, BRV displays a high and selective interaction with a novel brain-specific binding site SV2A (synaptic vesicle protein 2A). However, the binding affinity of BRV for SV2A is approximately 10 fold higher. This binding site appears to be the major target for its pharmacological activity. Unlike LEV, BRV also reduces voltage-dependent sodium currents. Brivaracetam also reverses the inhibitory effects of negative allosteric modulators on gamma-aminobutyric acid- and glycine induced currents. Brivaracetam is extensively metabolized, but seizure protection appears to be associated with the parent compound.

Brivaracetam is rapidly and completely absorbed throughout the gastrointestinal tract. The extent of BRV absorption is not affected by food. The PK is dose-proportional (at least from 10mg to 600mg). Brivaracetam is weakly bound to plasma proteins ( $\leq 20\%$ ). The volume of distribution is 0.5L/kg, a value that is close to that of total body water. The plasma half-life of BRV is approximately 8 hours in young healthy male adults. The main metabolic pathway of BRV is by hydrolysis of the acetamide group to the corresponding carboxylic acid, while a second pathway is the  $\omega$ 1-hydroxylation mediated by CYP2C19 (with contributions of several other isoenzymes). The combination of these 2 pathways results in the hydroxyacid terminal metabolite. These metabolites are not pharmacologically active. There is no evidence of chiral inversion of BRV. Brivaracetam is eliminated primarily by metabolism and by excretion in the urine. More than 95% of the dose, with less than 9% as unchanged BRV, is excreted in urine within 72 hours after dosing.

Pharmacokinetic studies in elderly and in subjects with renal impairment showed a similar PK profile of BRV compared to that in healthy subjects while the elimination of the metabolites was markedly slowed down. A PK study in subjects with hepatic impairment showed a 50% increase in exposure to BRV associated with decreased hydroxylation.

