### 7 STUDY TREATMENT(S)

### Description of investigational medicinal product(s) 7.1

Oral film-coated tablets of BRV 25mg, BRV 50mg, and matching PBO tablets will be used in

After an 8-Week Baseline Period and once the subject has fulfilled the eligibility criteria, he/she will be randomized to 50mg/day group, 200mg/day group or PBO group, and enter the double-blind Treatment Period (Visit 3 to Visit 7).

During the Treatment Period, subjects will be treated with BRV 50mg/day, BRV 200mg/day, or the matching PBO tablets in a double-blinded manner. Study medication should be given as 2 equally divided doses administered twice daily except the last week of down-titration. Study medication in the last week of down-titration is given only in the morning. The first intake of newly dispensed study medication should occur in the evening of each visit. Subjects should take IMP according to instructions provided by Investigator.

At the end of the Treatment Period (Visit 7), the subjects entering into the LTFU study or MAP will enter the Transition Period or the subjects not entering into the LTFU study or MAP will enter the Down-Titration Period followed by a Study Drug-Free Period.

The Transition Period (2 weeks) will consist of the following:

- For subjects randomized to BRV 50mg/day group or PBO group, keep same dose as Treatment Period during the Transition Period.
- For subjects randomized to BRV 200mg/day group, the Transition Period will consist of the • following: 2 weeks at BRV 150mg/day.

The Down-Titration Period (4 weeks) will consist of the following:

- For subjects randomized to PBO group, keep PBO during the Down-Titration Period.
- For subjects randomized to BRV 50mg/day group, the Down-Titration Period will consist of the following: 1 week at BRV 25mg/day followed by 3 weeks at PBO.
- For subjects randomized to BRV 200mg/day group, the Down-Titration Period will consist of the following: I week at BRV 150mg/day, 1 week at BRV 100mg/day, 1 week at BRV 50mg/day, followed by 1 week at BRV 25mg/day.

The down-titration procedure needs to be applied in case of early discontinuation or completion without conversion to the LTFU study or MAP.

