# **BRV Plasma Levels**

For BRV plasma levels, the date and time of the last 3 actual intakes will be recorded in the source documentation and eCRF.

One blood sample per visit should be obtained for BRV plasma levels at Visit 4, Visit 5, Visit 6, Visit7, and Visit 8 (Transition Period) or EDV. The Investigator should attempt as far as practically feasible to collect the sample at different times postdose in order to cover the 0 to 12 hour dosing interval (for example, between 0 to 2 hours postdose, 2 to 4 hours postdose, 4 to 8 hours postdose, and 8 to 12 hours postdose).

Brivaracetam plasma levels will be assayed in batch runs. Results of BRV plasma level measurements will only be communicated to the Investigator and UCB study team after database lock.

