3.5.6 Pharmacokinetic Per Protocol Set

The Pharmacokinetic Per-Protocol Set (PK-PPS) will consist of all subjects who took at least 1 dose of BRV and for whom at least 1 valid BRV plasma concentration-time record and dosing information are available.

Treatment assignment and treatment groups 3.6

All analyses will be based on randomized treatment group. Incorrectly treated subjects will be evaluated during the blinded DEM to assess the potential impact of such cases and any special considerations for statistical analyses. In general, subjects will be analyzed according to the planned treatment dose for efficacy analyses and according to the actual treatment dose for safety and PK analyses.

The labels used in presentations will be:

3.7

, cts Not randomized All BRV (BRV 200mg/day + BRV 50mg/day) Site pooling strategy number of randomized subjects for 1 not be feasible to adjust of udy outcomes by site The number of randomized subjects for most investigator sites is expected to be low. In general, it will not be feasible to adjust statistical analyses for site effect and there are no plans to present any study outcomes by site. No site pooling strategy is defined for this study.

Coding dictionaries 3.8

Medical history and adverse events (AEs) will be coded using the Medical Dictionary for Regulatory Activities (MedDRA) version 18.1. Medications will be coded using the World Health Organization Drug Reference List (WHO-DRL) version SEP 2017. Medical procedures will not be coded.

Definitions of study-specific derived variables 3.9 Lengths of study periods 3.9.1

Number of days in Baseline Period = date of day before Visit 3 - date of Visit 1.

Note that the 0.5 day is attributed from the day of Visit 3 which is considered part of the Baseline Period, and 0.5 days from the day of Visit 1 which is also considered part of the **Baseline** Period

Number of days in Treatment Period = date of Visit 7 (or EDV) – date of Visit 3.

Note that the first and last day of treatment period are considered as half days.

A similar calculation formula to the Treatment Period is applied to other post-treatment periods.

Lach seizure code in the clinical database will be mapped to exactly 1 of the following codes based on the International League Against Epilepsy (ILAE) classification (1981): IA (IA1, IA2, IA3, and IA4), IB, IC, II (IIA, IIB, IIC, IID, IIE, and IIF) or III. With regard to cluster seizures. investigate

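### The last PK time window in SAP 9.1 has no upper limit, so any sample taken after the 12-hour dosing interval is averaged with in-interval samples

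*SAP*

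**What the plan says.** SAP 9.1 groups concentrations into the windows ">0-4 hours, >4-8 hours, and >8 hours", timed "based on the date and time of last intake of IMP prior to blood sampling". The same three windows serve the descriptive statistics (observed and dose-normalised), the geometric-mean figures and the subject listing. The analyses are repeated for Japanese and Non-Japanese subjects.

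Protocol Section 7 gives study medication as two "equally divided doses administered twice daily", apart from the last week of down-titration, so the dosing interval is 12 hours. The protocol text on BRV plasma levels (Section 11.2) asks the investigator, as far as is practical, to vary the sampling time "in order to cover the 0 to 12 hour dosing interval". It offers 8 to 12 hours as an example of the last slot. One sample is due at each of Visits 4 to 7 and at "Visit 8 (Transition Period) or EDV".

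Three other rules bear on which samples enter the summary:

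- SAP 3.5.6 admits a subject to the PK set if "at least 1 valid BRV plasma concentration-time record and dosing information are available". This works at subject level, and the SAP does not define a valid record.
- SAP 3.1.1 replaces a value below the quantification limit by half that limit and keeps it.
- SAP 9.1 withholds the statistics only when fewer than two thirds of the values are at or above that limit.

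None of these refers to time since the last dose.

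**The concern.** The clock starts at the actual last intake. If the most recent scheduled dose was missed and not yet made up when blood is drawn, the recorded time passes 12 hours and the sample goes into the last window. So does a sample from an early discontinuation visit held after the subject had already stopped treatment. Concentrations at those times belong to continued elimination beyond the dosing interval, but they are averaged with samples from 8 to 12 hours.

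A geometric mean is sensitive to low values, so a few such samples can pull it down. The mean figures plot it against the median time in the window. A few late samples hardly move a median, so the plotted point would sit at roughly the usual time with a lowered concentration. At stake is a clean description of exposure late in the interval, in a study meant to support applications in Japan and China.

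**Working it through.** The plan states no figure on this point, so there is nothing to reproduce. The check asks how far late samples could move the geometric mean.

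**Inputs from the documents**

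- Half-life: "The plasma half-life of BRV is approximately 8 hours in young healthy male adults" (Protocol 2.2). Base case h = 8 h.
- Slower elimination: clearance of 0.70 against 0.99 mL/min/kg in subjects with two nonfunctional CYP2C19 alleles (Protocol 2.5). If volume is unchanged, h = 8 × 0.99/0.70 = 11.3 h.
- Faster elimination: rifampicin doubles clearance (Protocol 2.2). If volume is unchanged, h = 8/2 = 4 h.

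**Assumptions that the documents do not supply**

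- First-order decline from steady state.
- In-interval samples centred at 10 h, the midpoint of 8 to 12 h.
- A share f of the window's samples taken at a later time t. With one missed dose, t can reach 24 h, just before the next dose is due.

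**Formulas**

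- Late concentration relative to 10 h: r = 2^(−(t − 10)/h).
- Relative change in the geometric mean: r^f − 1.

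**Base case.** For t = 24 h and h = 8 h, r = 2^(−14/8) = 0.297. With f = 10%, 0.297^0.10 = 0.886, a fall of 11.4%. The other cases follow in the same way:

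| h (hours) | t (hours) | r | f | Change in geometric mean |
|---|---|---|---|---|
| 8 | 24 | 0.297 | 1% | −1.2% |
| 8 | 24 | 0.297 | 5% | −5.9% |
| 8 | 24 | 0.297 | 10% | −11.4% |
| 11.3 | 24 | 0.424 | 10% | −8.2% |
| 4 | 24 | 0.088 | 10% | −21.5% |
| 8 | 14 | 0.707 | 10% | −3.4% |

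The arithmetic mean, which SAP 3.1.1 also reports, moves less. With f = 10%, t = 24 h and h = 8 h, the change is 0.10 × (0.297 − 1) = −7.0%.

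Substitution of half the quantification limit is left out. The limit is not given, so one cannot tell whether late samples would fall below it.

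If the window is cut at 12 h, late samples have no effect on the >8-12 h row, by construction.

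**The case against.** The strongest reply is that the plan mislabels nothing and that late samples should be uncommon. Much of this stands, and it rules out several stronger readings.

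- **The SAP misreports a trough.** A reader might infer this, but the SAP never calls the last window a trough or an end-of-interval value. The row says what it contains.
- **The SAP contradicts the protocol.** It does not. The protocol's 8 to 12 hour slot is an example within sampling guidance, not an analysis window.
- **Samples at the early discontinuation visit are mostly washout samples.** The documents point the other way. Protocol Section 7 applies down-titration to early discontinuation, and Table 5-1 dispenses medication at that visit and sends the subject on to down-titration. A subject following the plan is normally still dosing. The exceptions are cases such as immediate liver-related discontinuation (Protocol 6.3.1) or a subject who stopped unprompted. No PK sample is scheduled in the Down-Titration or Study Drug-Free Periods.
- **The Japanese and Non-Japanese summaries are distorted against each other.** Nothing in the documents suggests that late sampling differs between these groups.

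It is also fair that the share of late samples is unknown, that Protocol 11.2 says intake must not be delayed for sampling, and that slightly late samples matter little. The listing and the individual plots show actual hours since intake, so a careful reader could spot late samples.

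That visibility does not repair the tables and mean figures, where late samples remain pooled. The undefined validity criterion and the outlier review before database lock (SAP 3.1) might remove some records, but neither is a prespecified rule on time since dose. Protocol 7.7 treats consumption of 80% to 120% as compliant, so some missed doses are within plan.

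**Conclusion.** The point holds as a small improvement to the descriptive PK analysis. The last window is unbounded, nothing separates samples taken after the 12-hour interval, and under declining concentrations such samples can only lower its geometric mean.

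The size is conditional. With an 8-hour half-life and a 10-hour reference, 1%, 5% or 10% of samples at 24 hours lowers the geometric mean by about 1%, 6% or 11%. At 10%, the fall runs from 8% to 21.5% for half-lives from 11.3 down to 4 hours. If the late samples lie near 14 hours, 10% of them costs only about 3%. These shares and times are assumptions; if late samples turn out to be rare, the effect is negligible.

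A reader should not infer any effect on efficacy results, type I error or sample size. The windows feed only the descriptive PK tables, the mean figures and the listing.

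**What to change.** In SAP 9.1, replace the last window by two, >8-12 hours and >12 hours, in the tables, the mean figures and the listing. If a tolerance is wanted for samples taken just past 12 hours, state it as a number before unblinding. Every sample stays in the summary, but post-interval samples are no longer averaged with in-interval ones.

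No new data are needed. Sampling times and the last three intake times are already recorded in the eCRF (Protocol Table 5-1 and Section 11.2). Concentrations are released only after database lock, so the number of samples beyond 12 hours can be counted beforehand without seeing any result.

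The cost is a wording change and one more row per table with few samples in it. That row may sometimes be suppressed by the two-thirds rule, in which case the listing carries the values. The split does not address a subject who missed a dose, took the next one and was then sampled within 12 hours. That sample stays in its window at a somewhat lower level.
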